### **11.4.4 Efficacy Analysis Plan**

Primary analysis:

The primary analysis is estimating the proportion of subjects with asymptomatic congenital CMV infection who, following treatment with 4 months of oral valganciclovir, develop SNHL by 6 months of life in at least one ear. Due to the small expected number of subjects who will develop SNHL by 6 months, the Clopper-Pearson method will be used to calculate an exact 95% upper confidence bound for the primary outcome.

Secondary analyses:

---

For the proportion of subjects who develop SNHL at 4, 12, and 18 months post baseline, we will also use the Clopper-Pearson method to obtain an estimate of the 95% upper confidence bounds separately for each period. In each of these hearing outcomes, we will provide a breakdown on the degree of worsening (mild, moderate, severe). This method will also be used to define safety and tolerability of valganciclovir by estimating the incidence of adverse events of interest. If there is enough information in the data collected, we will use a large-sample method for estimating the 95% confidence interval of interest over the more conservative Clopper-Pearson method.

Analysis of actual viral load will be done using log base 10 transformation for both whole blood and plasma CMV viral loads. Undetectable viral load value will be replaced by a value of 10. To investigate the change over time, we will model the log base 10 viral load using mixed model to accommodate repeated measures. The covariance structure (selected among unstructured, exchangeable, autoregressive, exponential, and toeplitz) that best describes the correlation among the repeated measures over time will be selected using the AIC model selection index. Note that there will be 13 time points for which viral load will be measured. Hence, if time will be represented as discrete variables in the model, this will require spending 12 degrees of freedom in the model, which we believe is unnecessary. In our modeling we will represent time as a continuous variable and will consider fitting linear, quadratic, and cubic to approximate non-linear trends. The simplest model with a good fit based on the test of the coefficients, as well as the profile curves, will be selected. Modeling will be done separately for whole blood and plasma viral loads.

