The same method of modeling will be employed to compare the whole blood and plasma CMV viral loads. However, the outcome will be the difference between the whole blood and plasma CMV viral load values for each subject at each time point. If the differences over time are found to be modeled by a linear function and there is no evidence to show that the slope of this line is significantly different from zero, then there is no evidence to conclude a difference between the average viral loads based on whole blood and plasma. Otherwise, there is a difference and this difference will be examined and discussed in more details based on the results of the fitted model.

We will investigate the how viral load is related to hearing outcomes using generalized linear model for binary outcome at each time point relative to baseline hearing.

All tests will use a 5% significance level, i.e., p-values<0.05 will be considered significant.

Ganciclovir resistance will be assessed by molecular methodologies (e.g., deep sequencing, Sanger sequencing, PCR). Blood, urine, and saliva specimens will be obtained serially.

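### The viral-load covariance menu makes no explicit allowance for infants differing in slope, so the slope test stated at 5% can run at roughly 6–11% under assumed variances

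*Combined protocol and SAP*

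**What the plan says.** Section 11.4.4 states that "we will model the log base 10 viral load using mixed model to accommodate repeated measures". The covariance is "selected among unstructured, exchangeable, autoregressive, exponential, and toeplitz", and the best one "will be selected using the AIC model selection index". On time, the section says: "Note that there will be 13 time points for which viral load will be measured". It rejects discrete time as too costly in degrees of freedom and continues: "In our modeling we will represent time as a continuous variable". Linear, quadratic and cubic forms are considered. Whole blood and plasma are modelled separately.

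The same method is then applied to the within-infant difference between whole blood and plasma. If that difference is linear in time and there is "no evidence to show that the slope of this line is significantly different from zero", the plan finds no evidence that the two differ; otherwise it declares a difference. The threshold is explicit: "All tests will use a 5% significance level, i.e., p-values<0.05 will be considered significant".

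The section mentions no random slope, robust standard error or degrees-of-freedom method. It does not say whether autoregressive and Toeplitz go by visit number or by elapsed time. Visit number is the usual meaning, and the separate listing of exponential fits that reading.

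Section 3.2.3 lists viral load as an exploratory outcome, although 11.4.4 describes the model under its secondary analyses.

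**The concern.** If infants differ in how fast their viral load changes, the variance and covariance of the repeated measures depend on when the measurements are taken. Exchangeable, autoregressive, exponential and Toeplitz, as commonly fitted, have constant variance and correlations that depend at most on lag. Unstructured can represent the pattern, but AIC charges it for 91 parameters. With moderate slope variation the penalty can outweigh the gain in fit. AIC then keeps a structure that understates the uncertainty of the average slope.

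The protocol gives reason to expect such variation. Sections 4 and 8.2.2.1 provide for resistance testing in infants whose load rises on treatment. Section 6.3 allows drug to be held, reduced or stopped in individual infants. The model window also includes two months off drug.

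What is at stake is mainly the whole blood minus plasma decision, which section 11.4.4 turns on one slope test. In the separate whole blood and plasma models a decline on treatment is expected, so a false-positive rate under no slope says less there.

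**Working it through.** **1. The plan's own figure.** Section 7 schedules viral load at Days 1, 7, 14, 21, 28, 35, 42, 56, 70 and 84 and Months 4, 5 and 6: 10 + 3 = 13 visits, hence 12 degrees of freedom for discrete time. Both figures are reproduced. The gaps are 6, 7, 7, 7, 7, 7, 14, 14, 14, about 36, 30 and 30 days (30-day months assumed).

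**2. The AIC penalty.** Unstructured has 13 × 14 / 2 = 91 parameters; Toeplitz has 13. Unstructured must improve −2 log-likelihood by more than 2 × (91 − 13) = 156 to be preferred.

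**3. From standard error to error rate.** For a null slope, the large-sample rejection rate is 2 × [1 − Φ(1.96 × model SE / true SE)]. A rate of 10% corresponds to a ratio of 1.645 / 1.96 = 0.84. A standard error 14% too small gives 1.96 × 0.86 = 1.69, or about 9.2%.

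**4. Simulation.** The documents give no variance components, so all of these are assumed, in log10 units (slope SD per month). N = 176 is the evaluable sample and N = 218 the expected enrolment, both from section 11.2. There are 1,500 runs per cell with complete data, a linear mean with no true slope, maximum-likelihood fits, AIC choice and a Wald test at 1.96. Autoregressive and Toeplitz go by visit number. Monte Carlo error is about √(0.1 × 0.9 / 1,500) = 0.8 percentage points at 10%. Each cell shows N = 176 / N = 218.

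| Assumed SDs | Main AIC choice | As planned, % | Sandwich, % | Subject-level slope test, % |
|---|---|---|---|---|
| intercept 0.8, slope 0.1, error 0.4 | Toeplitz 91% / 78% | 11.2 / 9.7 | 6.2 / 5.9 | 5.1 / 4.3 |
| same, plus serial 0.4 (range 2 months) | Toeplitz 95% / 86% | 10.5 / 9.7 | 5.5 / 5.7 | 5.4 / 4.7 |
| intercept 0.3, slope 0.06, error 0.2 | unstructured 75% / 93% | 8.7 / 6.2 | 6.7 / 5.7 | 5.3 / 4.3 |
| intercept 0.8, slope 0.2, error 0.4, serial 0.4 (range 2 months), intercept-slope correlation −0.5 | unstructured 94% / 100% | 8.0 / 6.7 | 7.1 / 6.7 | 5.3 / 4.8 |
| intercept 0.8, slope 0.3, error 0.4 | unstructured 100% / 100% | 6.6 / 5.7 | 6.6 / 5.7 | 4.9 / 4.9 |
| intercept 0.8, no slope, error 0.4, serial 0.8 (range 2 months) | unstructured 67% / 88% | 8.0 / 6.7 | 6.9 / 6.6 | 5.3 / 5.0 |

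The subject-level test estimates one slope per infant and tests their mean, which here is equivalent to allowing a random slope.

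**5. Removing options only.** Dropping autoregressive and Toeplitz without adding a random slope sends AIC to unstructured almost always. The rate is then 6.6–7.5% at N = 176 and 5.7–6.9% at N = 218, reflecting the missing small-sample correction.

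**6. Breadth.** A large-sample calculation over 220 assumed covariances at N = 218 had AIC choosing Toeplitz in 105, unstructured in 74, exponential in 33, exchangeable in 8 and autoregressive in none. Rejection at the chosen structure ran from 0.8% to 15.3%, median 5.0%. It passed 10% in 8% of cases (12% at N = 176). Without a random slope the maximum was 7.9%. A further search at N = 176 took cases where Toeplitz would reject at 14.3–15.1% in large samples. In finite samples AIC mostly chose unstructured, and the rate was 7.7–9.0%.

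**7. Other assumed variances.**
- With 3,000 runs per case at 176 or 200 infants and moderate slope differences, AIC took Toeplitz in 77–91% of runs. The planned test rejected in 8.4–9.3%, against 4.8–5.1% with a sandwich error and 4.6–4.7% with the subject-level test.
- In the same set, no slope variation gave 4.9%. Where unstructured was chosen the rate was about 8%; the sandwich did not help (8.2%), while the subject-level test gave 5.8%.
- With intercept SD 0.3, error SD 0.3 and slope SD 0.03 (600 runs), AIC chose exchangeable in 71% / 61% of runs at N = 176 / 218, and the rate was 8.5% / 8.3%.

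**The case against.** The strongest reply is that the menu already contains unstructured, which assumes nothing about spacing, and exponential, which uses actual time, so AIC will find an adequate structure. That is right when slope variation is large: at slope SD 0.3 AIC took unstructured every time, at 6.6% and 5.7%. It fails in the moderate range, where the 156-point penalty keeps Toeplitz.

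A reader might infer that visit-number indexing on uneven visits is the main cause. The calculations do not support that. Autoregressive was never chosen in the 220-case grid, and uneven spacing with serial correlation reaches at most about 8%. The larger inflation needs unmodelled slope variation. Indexing by visit number is itself an inference from usual practice.

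A reader might also take a doubling of the 5% as a bound or as the expected size. It is neither. It is a bad-case size under variances the documents do not supply; the grid median was 5.0% and some cases were conservative.

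Other replies stand in part. A mixed model could include random effects, so the text is silent rather than prohibitive; silence still does not secure 5%. Infant trajectories shared by whole blood and plasma should partly cancel in the difference, and no simulation was calibrated to that outcome. Effects on choosing linear, quadratic or cubic time were not simulated, and the plan uses profile curves as well as coefficient tests there. The outcomes are exploratory, and no stopping or treatment rule uses this slope.

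**Conclusion.** The point holds in limited form. As written, the AIC menu does not secure the stated 5% for the slope test. Across the six simulated cases the rate was 5.7–11.2%, highest where infants differ moderately in slope and AIC settles on Toeplitz. When AIC settles on unstructured, the test remains mildly liberal for want of a small-sample correction.

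These figures rest on assumed variances, complete data, a correct linear mean and no undetectable values replaced by 10. The practical consequence is a raised chance of declaring a whole blood versus plasma difference on a false slope. The primary Clopper-Pearson bound and the hearing-loss and safety estimates are not touched.

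**What to change.** In section 11.4.4, make a random intercept and random slope per infant, in actual study days, the core of the model. Offer exponential correlation in study days plus a measurement-error term as a candidate for the remaining correlation, in place of the visit-number Toeplitz and autoregressive options. State one inference method: Kenward-Roger degrees of freedom with model-based errors, or sandwich errors with a small-sample correction. Apply it to the whole blood, plasma and difference models.

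The random slope is the main change. The equivalent subject-level test held 4.3–5.4% in the six cases and 5.4–5.9% in the further search, whereas an uncorrected sandwich on the AIC-chosen model left 5.5–7.1% in the six cases. Section 8.2 ranks virology last when blood is short, so missed draws are likely, and a sandwich error does not by itself correct bias from a wrong covariance when data are missing. The full proposed model with Kenward-Roger was not itself simulated.

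The cost is a short edit to the plan, a software option, slightly more modelling work and slightly wider intervals. No new data are needed.

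### The exploratory whole-blood versus plasma rule combines up to three unadjusted 5% tests in an unstated order, so its false-positive rate can reach about 14%, and it words a trend test as a conclusion about average levels

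*Combined protocol and SAP*

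**What the plan says.** Section 11.4.4 (Efficacy Analysis Plan) first sets out how each fluid's log10 viral load is modelled over 13 time points: "In our modeling we will represent time as a continuous variable and will consider fitting linear, quadratic, and cubic to approximate non-linear trends". The shape is then chosen: "The simplest model with a good fit based on the test of the coefficients, as well as the profile curves, will be selected".

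For the comparison of the two fluids, "The same method of modeling will be employed to compare the whole blood and plasma CMV viral loads", with the whole-blood minus plasma difference for each subject at each time point as the outcome. The decision rule has two branches:

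- **No difference.** The condition begins "If the differences over time are found to be modeled by a linear function and there is no evidence to show that the slope" and requires that slope not to differ significantly from zero. The conclusion is then "no evidence to conclude a difference between the average viral loads based on whole blood and plasma".
- **Difference.** Everything else: "Otherwise, there is a difference and this difference will be examined and discussed in more details".

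The section adds: "All tests will use a 5% significance level, i.e., p-values<0.05 will be considered significant". It gives no order of testing, no adjustment and no overall error rate for the rule. Sections 3.1 and 3.2.3 list viral-load change in the two fluids as exploratory.

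**The concern.** The first branch has two conditions, a linear shape and a flat slope. Failing either one leads to the categorical statement that the fluids differ. The tests that choose the shape are therefore part of the decision, and a significant quadratic or cubic term is as decisive as a significant slope. Several chances at 5% are combined into one yes-or-no conclusion.

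There is a second problem in the same sentence. The conclusion is about average viral loads, but nothing in the rule tests the intercept. Two fluids that run parallel at clearly different levels would be reported as showing no evidence of a difference.

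At stake is how this exploratory comparison is reported. A divergence between the fluids could be announced more often than a reader who sees a 5% level would expect, and a stable gap could be passed over.

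**Working it through.** **Inputs.** Level 5% per test (Section 11.4.4; two-sided assumed, as sidedness is not stated). Candidate shapes: linear, quadratic, cubic. Visits: Days 1, 7, 14, 21, 28, 35, 42, 56, 70 and 84 and Months 4, 5 and 6 (Section 7), which reproduces the stated 13 time points; the months are taken as Days 122, 152 and 183. Sample size 176 (Section 11.2). The difference is taken to be on the log10 scale.

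**Single test.** A slope test alone has a false-positive rate of 1 − 0.95 = 5%, which is the plan's figure.

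**Combined rule.** With correct covariance weighting, the test of the highest term in the linear, quadratic and cubic fits uses three mutually orthogonal contrasts. Under no time trend the tests are therefore independent in large samples, and the chance that at least one of k is significant is 1 − 0.95^k:

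- k = 2 (slope, quadratic): 1 − 0.9025 = 9.75%
- k = 3 (slope, quadratic, cubic): 1 − 0.857375 = 14.26%

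**Simulation.** No time trend, n = 176, four correlation structures (exchangeable, independent, exponential, first-order autoregressive), covariance known, 40,000 runs each, with and without a constant offset:

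| Reading of the rule | False-positive rate |
|---|---|
| Quadratic tried only after a significant slope | 4.9–5.2% |
| Any coefficient in one full cubic fit, time counted from Day 1 | 7.0–7.9% |
| Slope or quadratic, in sequence | 9.6–9.9% |
| Slope, quadratic or cubic, in sequence | 14.1–14.5% |
| One joint 3-df test of the three terms | 4.8–5.3% |

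The second row depends on how time is coded. With centred time it rises to about 10–11%, still inside the overall range. With the variance estimated instead of known (exchangeable case, 6,000 runs), the two sequential readings give 9.7% and 14.1% at n = 176, and 10.0% and 14.5% at n = 60.

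**Constant gap.** With a constant offset of 0.5 and SD 1 (both assumed), the sequential and slope-only rates are unchanged at about 5 to 14%: the rule cannot see the gap. A joint 4-df test that includes the intercept detects it in every run and holds 4.8–5.2% when there is no difference at all.

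**The case against.** The strongest reply is that the 10–14% figure belongs to one procedure, and the plan does not fully specify a procedure. Selection rests on good fit and profile curves as well as coefficient tests, and no order is given. If the quadratic is tried only after a significant slope, the rate is 5%. If selection works upward and stops at a non-significant quadratic, it is 9.75%, not 14.3%. This stands, and the size must be given as a range. It does not remove the point. Linearity is a condition separate from the slope result, so the natural reading judges shape even when the slope is flat. An unstated order also leaves the error rate to a choice that can be made after seeing the data.

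A reader might infer that the plan contradicts a 5% error rate it promised for this conclusion. The text does not support that: 5% is the level of each test, and no rate is claimed for the rule as a whole.

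It is also fair to say that exploratory analyses often go without multiplicity control, and that a positive result here leads only to further examination and discussion. That stands and sets the priority. Finally, the simulations assume the correct covariance, whereas the plan selects among five structures by AIC and replaces undetectable values with 10. The figures isolate the effect of the rule and are not full operating characteristics of the planned analysis.

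**Conclusion.** The point holds as a minor one. Under no time trend, the rule's false-positive rate is not controlled at 5%: about 9.75% with two sequential tests, up to about 14.3% with three, and 5 to 8% under other readings. These figures assume two-sided tests, selection by coefficient tests alone and a correctly specified covariance; the effect of the visual element cannot be quantified. Separately, and whatever the testing order, the conclusion about average viral loads does not follow from a test of trend, because a constant gap falls in the no-difference branch.

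A reader might take this as a flat two- to threefold inflation, or as a threat to the trial's main result. The documents support neither. The multiple depends on an unstated order, and the Clopper-Pearson bound for sensorineural hearing loss does not use this model.

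**What to change.** Replace the two-branch rule in Section 11.4.4 with the following:

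1. Fit the log10 whole-blood minus plasma difference with linear, quadratic and cubic time in the mixed model. Test the three time coefficients jointly (one 3-df F or likelihood-ratio test) at 5%.
2. Word the conclusion as whether the change over time differs between whole blood and plasma, not whether average levels differ. This matches the exploratory objective in Section 3.1, which is about changes.
3. Report the mean difference with its 95% confidence interval separately, so that a constant gap is visible.
4. Use shape selection only afterwards, to describe and plot the difference.

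The joint test does not depend on the order of testing or on how time is centred.

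The cost is a few sentences and no new data, plus some power against a purely linear drift. For a drift that the 1-df slope test would detect with 80% power, the noncentrality is (1.96 + 0.84)² ≈ 7.85. The 3-df test (critical value 7.81) then has about 64% power. If that is too much to give up, the sequence could be kept with its order fixed in advance and the per-test level lowered to 1 − 0.95^(1/2) = 0.0253 for two tests or 1 − 0.95^(1/3) = 0.0170 for three.

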#### **11.4.5 Missing Values and Outliers**

Missing safety and/or hearing outcome data will not be imputed. No search for outliers will be performed.

---

## **12 SOURCE DOCUMENTS AND ACCESS TO SOURCE DATA/DOCUMENTS**

The investigator is responsible for ensuring the accuracy, completeness, legibility, and timeliness of the data reported.

Data reported in the eCRF derived from the data collection forms should be consistent with the source documents or the discrepancies should be explained.

Each site will permit authorized representatives of the DMID, its designees, and appropriate regulatory agencies to examine (and when required by applicable law, to copy) clinical records for the purposes of quality assurance reviews, audits, monitoring, and evaluation of the study safety and progress. These representatives will be permitted access to all source data, which include, but are not limited to, review of informed consents, hospital records, clinical and office charts, laboratory notes, memoranda, evaluation checklists, pharmacy dispensing records, recorded data from automated instruments, copies or transcriptions certified after verification as being accurate and complete, microfiches, photographic negatives, microfilm or magnetic media, x-rays, and subject files and records kept at the pharmacy, at the laboratories, and medico-technical departments involved in the clinical trial. Data collection forms used as source documents will be derived from the eCRFs and be provided by the SDCC.

---

## 13 QUALITY CONTROL AND QUALITY ASSURANCE

Each study site will have a quality management plan. Following a written DMID-accepted site quality management plan, the investigational site is responsible for conducting routine quality assurance and quality control activities to internally monitor study progress and protocol compliance. The PI will provide direct access to all trial-related sites, source data/documents, and reports for the purpose of monitoring and auditing by the sponsor, and inspection by local and regulatory authorities. The PI will ensure all study personnel are appropriately trained and applicable documentation is maintained on site.

DMID-designated clinical monitors will verify that the clinical trial is conducted and data are generated, documented (recorded), and reported in compliance with the protocol, ICH/GCP guidelines, and the applicable regulatory requirements. Clinical monitoring reports will be submitted to DMID.

The SDCC will implement quality control procedures beginning with the data entry system and generate data quality control checks that will be run on the database. Any missing data or data anomalies will be communicated to the site(s) for clarification and resolution.

---

